89.6% and 75.8%, respectively, with SEL exposure resulting in half-maximal inhibition of 185 hr*ng/mL and 1520 hr*ng/mL, respectively. These analyses of ASK-1 engagement support dose selection of 18 mg SEL which provides near maximal effect and any further increased dose of SEL is not expected to provide meaningfully greater PD response, or increased efficacy.

Figure 1-4. PK/PD Relationships for SEL Exposure (AUC_{tau}) and %p-p38 or %p-ASK-1 (Study GS-US-223-1015)

Similar to p38 phosphorylation, in the Phase 2 DKD study, a dose- and exposure (AUC_{tau})-dependent response relationship was observed for the rate of eGFR decline (slope) from Week 4 to 48. The mean eGFR slope in the 18 mg group was -1.27 mL/min/1.73 m²/year, significantly smaller than the placebo group slope (-4.97 mL/min/1.73 m²/year), and residing on the flat portion of the dose- and exposure-response curves. Additionally, the relationship between p-p38 inhibition and chronic eGFR slope by dose group showed a trend in improved efficacy with increasing dose of SEL with minimal overlap between SEL 18 mg and placebo.

In the Phase 2 DKD study, there was a small difference in change in eGFR between the 6 mg and 18 mg doses of SEL that trended in favor of the 18 mg dose at 48 weeks but was not statistically significant. This improvement with the 18 mg dose in slowing the rate of eGFR decline may be clinically significant over longer periods of time. For example, for patients starting with an eGFR of 30 mL/min/1.73 m², this difference between doses would increase time to kidney failure from approximately 4 years with SEL 6 mg to approximately 6 years with SEL 18 mg. In the context of such large therapeutic differences and a disease course that spans many years, SEL 18 mg is the optimal dose for the long-term prevention of kidney failure among patients with moderate to advanced DKD.

Across the clinical development program, SEL administered for up to 48 weeks has been well tolerated with no clear exposure relationship for the incidence or severity of adverse events or laboratory abnormalities. Collectively, the efficacy, safety, and PK/PD data support evaluation of SEL 18 mg in this Phase 2b study in subjects with DKD.

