7.5.4. Liver Enzymes

To mitigate the potential risk of liver injury, subjects are monitored closely; defined rules for close observation and drug cessation due to elevated liver tests are specified.

After becoming aware of any of the following abnormal laboratory values, an unscheduled visit (ie, sequential visit) should occur to retest within 3 to 7 days of receipt of the original test results. Retest may be obtained sooner if medically indicated per investigator judgement.

If ALT and/or AST:

- > 3 – 5 x ULN (Grade 2): Monitor at least weekly until < or equal to 1.5 x ULN
- > 5 – 20 x ULN (Grade 3): Withhold study drug. Monitor at least weekly until ALT/AST are < or equal to 1.5 x ULN, then may resume study drug. If Grade 3 recurrence, withhold study drug. Monitor at least weekly until ALT/AST < or equal to 1.5 x ULN, then may resume study drug. If Grade 3 recurrence, discontinue study drug permanently
- > 20 x ULN (Grade 4): Withhold study drug until ALT/AST < or equal to 1.5 x ULN, then may resume study drug. If Grade 4 recurrence, discontinue study drug permanently

7.5.5. eGFR Decline

SEL is associated with an acute decline in eGFR after study drug initiation, and in the phase 2 study of SEL in DKD (GS-US-223-1015), the median acute eGFR decline associated with SEL 18 mg at Week 4 was 10%. We observed that approximately 25% of subjects had an acute eGFR decline of 19% or greater (25th percentile), and 75% of subjects had an acute eGFR decline of 4% or greater (75th percentile).

However, acute declines in eGFR are expected to occur in subjects with moderate to advanced DKD and may not necessarily be associated with SEL. If acute eGFR decline occurs after the period following study drug initiation, refer to the below instructions:

- If clinically indicated, evaluate for alternative etiologies of eGFR decline and address reversible factors
- Avoid withholding or discontinuation of study drug in the setting of eGFR decline to the extent possible
- Consult with Gilead Medical Monitor and/or sponsor designee prior to withholding or discontinuing study drug
- If study drug is withheld, restart study drug as soon as clinically appropriate and check eGFR at next scheduled visit, preferably with study drug taken for at least 7 consecutive days.

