 - In general, the last nonmissing value on or prior to the first dosing date of Run-in SEL will be selected, unless specified differently. If there are multiple records with the same time or no time recorded on the same day, the Baseline value will be the average of the measurements for continuous data, or the measurement with the lowest severity (e.g., normal will be selected over abnormal for safety electrocardiogram (ECG) findings) for categorical data.
 - For eGFR_{cr}, eGFR_{cys}, UACR (including urine albumin, urine creatinine), serum creatinine and serum cystatin C, a single value within each of the Visit A and/or Visit B analysis window will be used to calculate pre-run-in and/or post-run-in Baselines.
 - Within each analysis window, the latest record will be selected.
 - If there is more than 1 record on the selected day, the record with the latest time will be selected. If all records have the same time, or time is missing for at least one record, the average will be taken.
- For post-SEL-treatment values (Visit C, Day 1 and post-Randomization visits):
 - The record closest to the nominal day for that visit will be selected.
 - If there are 2 records that are equidistant from the nominal day, the later record will be selected.
 - If there is more than 1 record on the selected day, the record with the latest time will be selected. If all records have the same time, or time is missing for at least one record, the average will be taken.

Definition of pre-run-in Baseline: The average of the measurements at Visit A and Visit B.

Definition of post-run-in Baseline: The average of the measurements at Visit C and Day 1.

Definition of treatment-specific Baselines: For subjects in the placebo arm, Baseline is defined as pre-run-in Baseline. For subjects in the SEL arm, Baseline is defined as post-run-in Baseline.

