7.2.1. Summaries of Numeric Laboratory Results

Descriptive statistics will be provided by treatment group for each central laboratory test specified in the study protocol as follows:

- Baseline values
- Values at each postbaseline visit
- Change from Baseline at each postbaseline visit

A Baseline laboratory value will be defined as the last nonmissing measurement obtained on or prior to the date/time of first dose of Run-in SEL, with the exception that Baseline laboratory values for serum creatinine, serum cystatin C, eGFR_{cr}, eGFR_{cys}, urine albumin, urine creatinine and UACR will be defined as the average values of Visit A and Visit B measurements. Change from Baseline to a postbaseline visit will be defined as the visit value minus the Baseline value. The mean, median, Q1, Q3, minimum, and maximum values will be displayed to the reported number of digits; SD values will be displayed to the reported number of digits plus 1.

Median (Q1, Q3) of the change from Baseline values for white blood cells, neutrophils, lymphocytes, hemoglobin, platelet count, serum creatinine, eGFR_{cr}, serum cystatin C, eGFR_{cys}, UACR, total bilirubin, aspartate aminotransferase (AST), alanine aminotransferase (ALT) and alkaline phosphatase (ALP) will be plotted using a line plot by randomization status, treatment group and visit.

In the case of multiple values in an analysis window, data will be selected for analysis as described in Section 3.8.3.

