7.2.2. Graded Laboratory Values

The modified CTCAE v5.0 criteria as specified in the protocol will be used for assigning toxicity grades (0 to 4) to central laboratory results for analysis.

Severity grading for serum creatinine will be defined with the following criteria for reporting purposes. Any serum creatinine within the normal range should be grade 0 regardless of the criteria specified.

Grade 1	Grade 2	Grade 3	Grade 4
1.25 to < 1.5 x Baseline	1.5 to < 1.75 x Baseline	1.75 to ≤ 3 x Baseline	>3 x Baseline

Severity grading for serum cystatin C will be defined with the following criteria for reporting purposes. Any serum cystatin C within the normal range should be grade 0 regardless of the criteria specified.

Grade 1	Grade 2	Grade 3	Grade 4
1.25 to < 1.5 x Baseline	1.5 to < 1.75 x Baseline	1.75 to \leq 3 x Baseline	>3 x Baseline

Grade 0 includes all values that do not meet the criteria for an abnormality of at least Grade 1. For laboratory tests with criteria for both increased and decreased levels, analyses for each direction (ie, increased, decreased) will be presented separately.

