7.2.2.1. Treatment-Emergent Laboratory Abnormalities

Treatment-emergent laboratory abnormalities are defined as follows for SEL and placebo exposures, respectively. Treatment-emergent laboratory abnormalities will only be evaluated for central laboratory testing results.

- SEL exposure: values that increase at least 1 toxicity grade from Baseline at any time point after the first dosing date of Run-in SEL, up to and including the date of last dose of SEL plus 30 days.
- Placebo exposure: values that increase at least 1 toxicity grade from Baseline at any time point on or after Study Day 31, up to and including the date of last dose of Randomized placebo plus 30 days.

Baseline is defined as the last nonmissing value prior to the first dose of Run-in SEL.

If the relevant Baseline laboratory value is missing, any abnormality of at least Grade 1 observed within the time frame specified above will be considered treatment emergent.

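### The SAP gives two baselines for serum creatinine and serum cystatin C and does not say which one sets their toxicity grades

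*SAP*

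**What the plan says.** SAP 7.2.1 takes the last value on or before the first run-in dose of selonsertib (SEL) as the general laboratory baseline. It then lists exceptions, among them serum creatinine and serum cystatin C, whose baselines "will be defined as the average values of Visit A and Visit B measurements". SAP 3.8.3 gives the same average as the pre-run-in baseline: "Definition of pre-run-in Baseline: The average of the measurements at Visit A and Visit B".

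SAP 7.2.2 grades both analytes by ratio. Grade 1 is "1.25 to < 1.5 x Baseline", Grade 2 starts at 1.5, Grade 3 at 1.75, and Grade 4 lies above 3 times baseline. That section does not define the baseline. It adds a normal-range rule: "Any serum creatinine within the normal range should be grade 0 regardless of the criteria specified"; cystatin C has the same rule.

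SAP 7.2.2.1 (a rise of at least one grade) and 7.2.2.2 (marked, at least two grades) each close with the same definition: "Baseline is defined as the last nonmissing value prior to the first dose of Run-in SEL". Neither repeats the exception. SAP 7.2.2.3 reports the resulting numbers and EAIRs by exposure type.

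**The concern.** For most tests the baseline matters only for the shift. For these two it also fixes the grade, because the cut-offs are ratios to it. A programmer who follows 7.2.2.1 divides by one value, in practice the Visit B pre-dose sample. A programmer who carries 7.2.1 forward divides by the mean of two. Both have text to point to.

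The tests are kidney safety measures for a drug with a known early effect on eGFR: Protocol 7.5.5 reports that in the earlier Phase 2 study "the median acute eGFR decline associated with SEL 18 mg at Week 4 was 10" percent. A rise of that order brings many subjects close enough to the Grade 1 cut-off for baseline noise to decide the flag.

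**Working it through.** **Plan's own figure.** The SAP gives no number that depends on the laboratory baseline, so there is none to reproduce.

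**Inputs from the documents.** Cut-offs 1.25 and 1.5 (SAP 7.2.2). Visits at Weeks 4, 8, 12, 24, 36, 48, 60, 72 and 84. Acute eGFR fall of 10% on SEL (Protocol 7.5.5). Chronic slopes of -1.27 (SEL 18 mg) and -4.97 (placebo) mL/min/1.73 m²/year (Protocol 1.4). CKD-EPI creatinine exponent -1.209, so a 10% fall is a creatinine ratio of 0.9^(-1/1.209) = 1.091. The earlier study used MDRD eGFR, so this conversion is approximate; with the MDRD exponent it is 0.9^(-1/1.154) = 1.096.

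**Assumptions not in the documents.** Within-subject CV 5% to 10%, independent log-normal errors, starting eGFR 35.

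**Step 1: one post-baseline value, no true change.** The log ratio has SD CV×√2 with a single baseline and about CV×√1.5 with a two-visit average. P(ratio ≥ 1.25) = 1 - Φ(ln 1.25 / SD), with ln 1.25 = 0.2231.

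- CV 5%: 0.2231/0.0707 = 3.16, giving 0.08%; 0.2231/0.0612 = 3.64, giving 0.01%.
- CV 7.5%: 0.2231/0.1061 = 2.10, giving 1.8%; 0.2231/0.0919 = 2.43, giving 0.8%.
- CV 10%: 0.2231/0.1414 = 1.58, giving 5.7%; 0.2231/0.1225 = 1.82, giving 3.4%.

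**Step 2: at least one crossing over follow-up.** Simulation of 400,000 subjects per scenario; the SEL scenario also counts two run-in SEL values. With baseline at Grade 0, Grade 1 or above is what makes a value treatment-emergent and Grade 2 or above is what makes it marked. Percent of subjects, single / average baseline:

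| Scenario | CV | Grade ≥1 | Grade ≥2 |
|---|---|---|---|
| Stable | 5% | 0.6 / 0.1 | 0.0 / 0.0 |
| Stable | 7.5% | 10.1 / 5.4 | 0.1 / 0.0 |
| Stable | 10% | 25.9 / 20.0 | 1.5 / 0.4 |
| Placebo slope | 5% | 56.3 / 56.9 | 0.4 / 0.1 |
| Placebo slope | 7.5% | 63.7 / 65.7 | 5.6 / 2.8 |
| Placebo slope | 10% | 68.8 / 71.7 | 15.8 / 10.6 |
| SEL: 10% fall, then -1.27/year | 5% | 30.5 / 25.7 | 0.0 / 0.0 |
| SEL | 7.5% | 53.4 / 53.2 | 2.4 / 0.8 |
| SEL | 10% | 65.3 / 68.0 | 12.0 / 6.9 |

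**Step 3: why the Grade 1 count can reverse.** At the placebo slope, eGFR 35 becomes 35 - 4.97×84/52 = 26.97 by Week 84, a true creatinine ratio of (35/26.97)^(1/1.209) = 1.24. The subject's highest observed ratio is then centred near or above 1.25, and extra baseline noise pushes some true crossers back below it. A subject centred well below 1.25 can only gain flags.

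**Step 4: subject-level error.** Compare each flag with the one obtained by dividing the same post-baseline values by the subject's true baseline. With the 10% dip and no slope, Grade 1 or above is misclassified in 13.6% (single) against 8.1% (average) at CV 5%, and in 28.2% against 22.1% at CV 7%. The two baselines disagree with each other in 10.5%, 18.7% and 20.9% of subjects at CV 5%, 7% and 10%.

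**Step 5: the mixed reading.** Suppose grades use the average B̄ = (A+B)/2 and only the shift starts from the grade of the last value B. B is itself Grade 1 only if B ≥ 1.25×(A+B)/2, that is B ≥ 1.67×A, which is rare. In the simulation the Grade 1 results then match the all-average results within 0.4 points, at every CV up to 15%.

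**The case against.** The strongest reply is that 7.2.2 never names the single value as denominator. The section just before it defines the baseline for these two tests by name, and the sentence in 7.2.2.1 can be read as governing only the shift. On that reading Step 5 shows that essentially nothing is added. This stands as a possible reading, but the baseline sentences in 7.2.2.1 and 7.2.2.2 are unqualified and the SAP does not say which reading applies.

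A reader might infer that the single value generally adds false abnormalities. The documents do not support that. The net Grade 1 count falls slightly in subjects declining at the placebo slope from eGFR 35 (62.4% against 64.2% at CV 7%). From eGFR 45 it rises (42.6% against 40.0%).

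A reader might also infer bias toward one arm. The same baseline rule applies to both exposures, so it has no direction of its own, although its effect can differ with trajectory and exposure time.

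The size depends on an assumed CV. The simulation also ignores the normal-range rule, which can only lower counts. It counts Week 4 (nominal Day 29) for placebo, whereas SAP 7.2.2.1 starts placebo at Study Day 31. The figures are for creatinine; the noise argument carries over to cystatin C, the numbers do not.

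Disagreement with the change-from-baseline table is a weak harm: that table is by visit and treatment group, the graded one by worst grade and exposure type. They would not tie after the change either.

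**Conclusion.** The point holds as an inconsistency and an unspecified denominator. It does not establish that the SAP grades against the single value, or that such grading inflates every count.

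If the single value is used, subject-level grades are noisier. In the scenarios above, where Grade 2 or above reaches at least 1% with the single value, its frequency is 1.5 times (15.8/10.6) to about 4 times (1.49/0.37) that with the average. These figures rest on the assumed 5% to 10% CV and the other simulation assumptions, so they illustrate scale and do not predict the trial's tables.

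The reach is narrow: numbers and EAIRs of graded creatinine and cystatin C abnormalities. SAP 7.2 plans no formal testing of laboratory data. Efficacy endpoints and power do not use this baseline, and the change-from-baseline summaries in 7.2.1 already use the average. This is a minor point, worth settling because the SAP already contains the better rule.

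**What to change.** In SAP 7.2.2, and by reference in 7.2.2.1 and 7.2.2.2, state that for serum creatinine and serum cystatin C the baseline for both the grade denominator and the grade shift is the Visit A/Visit B average, as in 7.2.1. The last-value rule stays for all other graded tests.

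The cost is one sentence. Both samples are already collected and the average is already derived for 7.2.1. It should be settled before unblinding, so that the choice cannot follow the results.

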7.2.2.2. Treatment-Emergent Marked Laboratory Abnormalities

Treatment-emergent marked laboratory abnormalities are defined as follows for SEL and placebo exposures, respectively. Treatment-emergent marked laboratory abnormalities will only be evaluated for central laboratory testing results.

- SEL exposure: values that increase at least 2 toxicity grades from Baseline at any time point after the first dosing date of Run-in SEL, up to and including the date of last dose of SEL plus 30 days.
- Placebo exposure: values that increase at least 2 toxicity grades from Baseline at any time point on or after Study Day 31, up to and including the date of last dose of Randomized placebo plus 30 days.

Baseline is defined as the last nonmissing value prior to the first dose of Run-in SEL.

If the relevant Baseline laboratory value is missing, any Grade 2, 3 or 4 values observed within the time frame specified above will be considered treatment emergent.

7.2.2.3. Summaries of Laboratory Abnormalities

Laboratory data that are categorical will be summarized using the number and percentage of subjects in the study with the given response at Baseline and each scheduled postbaseline visit.

The following summaries (number and EAIR per 100 Patient Years) for treatment-emergent central laboratory abnormalities will be provided by lab test and exposure type (SEL or placebo); subjects will be categorized according to the most severe postbaseline abnormality grade for a given lab test:

- Treatment-emergent laboratory abnormalities
- Treatment-emergent Grade 3 or 4 laboratory abnormalities
- Treatment-emergent marked laboratory abnormalities

EAIR for treatment-emergent laboratory abnormalities will be calculated in the same manner as EAIR for TEAEs (Section 7.1.6.2).

A by-subject listing of treatment-emergent Grade 3 or 4 laboratory abnormalities will be provided by subject ID number and visit in chronological order. This listing will include all test results that were collected throughout the study for the lab test of interest, with all applicable severity grades displayed.

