 Factors:

- eGFR Strata:

eGFR (mL/min/1.73 m ²)
≥ 45
≥ 30 to < 45
≥ 15 to < 30

- Albuminuria Strata: UACR < 1500 mg/g vs. ≥ 1500 mg/g
- Concomitant SGLT-2 Inhibitor Use Strata: Yes vs. No

Randomization will be stratified by the average eGFR values from Visit A and Visit B; the average values of UACR from Visit A and Visit B; and concomitant use of SGLT-2 inhibitors assessed at Visit 1. Visit A and B values for eGFR and Albuminuria will be transferred directly from the central laboratory to the interactive web response system (IWRS) for stratification but eGFR values will not be released to sites, investigators, or the sponsor.

Study Procedures/
 Frequency:

Subjects who meet eligibility criteria at Screening will enroll into the Run-in period. Starting at Visit A, subjects will receive PTM once daily for at least 7 consecutive days. Starting at Visit B, subjects will begin to receive SEL (18 mg) once daily for at least 4 weeks.

During the Run-in period, subjects will be monitored for safety and study drug compliance. After Enrollment (Visit A), subjects will be required to return to the study site on Visit B (7-14 days after Visit A), Visit C (21-28 days after Visit B), and Visit 1 (7-14 days after Visit C). Immediately prior to Visit C and Visit 1, subjects must be on SEL for at least 7 consecutive days. Visit windows are provided in the unlikely event that a subject misses a dose within 7 days prior to Visit C and Visit 1.

Following the Run-in period, eligible subjects will be randomized at the study site on Visit 1 to enter the blinded treatment phase. Subjects will have study visits on Weeks 4, 8, 12, 24, 36, 48, and every 12 weeks thereafter. SEL/PTM will continue to be administered until kidney failure (dialysis performed for at least 4 weeks, kidney transplantation, or confirmed decrease in eGFR to <15 mL/min/1.73 m² for subjects without dialysis or kidney transplantation), death, study drug discontinuation (e.g., unacceptable toxicity, subject’s refusal of treatment, kidney transplantation), or the global study end date.

Subjects who permanently discontinue study drug prior to the global study end date will have an EOT visit and a 30 Day (± 7 days) EOT Follow-up visit. They will then resume all study visits per the schedule of procedures and attend all subsequent study visits in the same manner as subjects who are still receiving study drug.

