7.1.6.1. Calculation of Treatment Exposure

Treatment exposure will be calculated as follows, for SEL and placebo respectively:

- SEL: Total exposure (Patient Year) is calculated as the sum of Run-in SEL and Randomized SEL exposure time (in years) for all subjects who have been exposed to Run-in SEL and/or Randomized SEL in the Safety Analysis Set, starting from the first dosing date of Run-in SEL to the last dosing date of SEL (Run-in SEL or Randomized SEL).

In other words,

Total SEL Exposure

$$\begin{aligned}
 &= \sum_{i \in \{\text{Subjects randomized to SEL}\}} \text{Ex}(\text{first dose of Runin SEL to last dose of Randomized SEL})_i \\
 &+ \sum_{i \in \{\text{Subjects randomized to Placebo}\}} \text{Ex}(\text{first dose of Runin SEL to last dose of Runin SEL})_i \\
 &+ \sum_{i \in \{\text{Subjects not randomized}\}} \text{Ex}(\text{first dose of Runin SEL to last dose of Runin SEL})_i
 \end{aligned}$$

- Placebo: Total exposure (Patient Year) is calculated as the sum of Randomized placebo exposure time (in years) for all subjects who exposed to Randomized placebo in the Safety Analysis Set, starting from Study Day 1 to the last dosing date of Randomized placebo.

In other words,

Total Placebo Exposure

$$= \sum_{i \in \{\text{Subjects randomized to Placebo}\}} \text{Ex}(\text{first dose of Randomized Placebo to last dose of Randomized Placebo})_i$$

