7.2.3. Liver-related Laboratory Evaluations

Liver-related abnormalities after initial study drug dosing will be examined and summarized using the number and EAIR of subjects who were reported to have the following central laboratory test values for postbaseline measurements:

- AST: (a) > 3 times of the upper limit of reference range (ULN); (b) > 5 x ULN; (c) > 10 x ULN; (d) > 20 x ULN
- ALT: (a) > 3 x ULN; (b) > 5 x ULN; (c) > 10 x ULN; (d) > 20 x ULN
- AST or ALT: (a) > 3 x ULN; (b) > 5 x ULN; (c) > 10 x ULN; (d) > 20 x ULN
- Total bilirubin: (a) > 1 x ULN; (b) > 2 x ULN
- ALP: > 1.5 x ULN
- AST or ALT > 3 x ULN and (a) total bilirubin > 1.5 x ULN; (b) total bilirubin > 2 x ULN; (c) total bilirubin > 2 x ULN and ALP < 2 x ULN

The summary will include data for the following exposure periods for SEL and placebo exposures, respectively:

- SEL exposure: at any time point after the first dosing date of Run-in SEL, up to and including the date of last dose of SEL plus 30 days.
- Placebo exposure: at any time point on or after Study Day 31, up to and including the date of last dose of Randomized placebo plus 30 days.

For individual laboratory tests, subjects will be counted once based on the most severe values in corresponding period. For both the composite endpoint of AST or ALT and total bilirubin, subjects will be counted once when the criteria are met at the same postbaseline visit date. A listing of subjects who met at least 1 of the above criteria will be provided.

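### Laboratory and liver-test rates per exposure-year credit SEL with the densely sampled run-in, so with no drug effect the SEL:placebo ratio runs from about 1.0 to 1.8, depending on how long abnormalities last

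*SAP*

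**What the plan says.** **Formula.** SAP 7.1.6.2 divides the number of subjects with at least one event by total exposure time. Section 7.2.2.3 carries this over: "EAIR for treatment-emergent laboratory abnormalities will be calculated in the same manner as EAIR for TEAEs (Section 7.1.6.2". It applies to all treatment-emergent, Grade 3-4 and marked abnormalities. Section 7.2.3 extends it to liver tests, "summarized using the number and EAIR of subjects who were reported to have the following central laboratory test values".

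**Numerators (SAP 7.2.2.1, 7.2.2.2, 7.2.3).** SEL abnormalities count "after the first dosing date of Run-in SEL, up to and including the date of last dose of SEL plus 30 days". Placebo starts later: "Placebo exposure: values that increase at least 1 toxicity grade from Baseline at any time point on or after Study Day 31".

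**Denominators (SAP 7.1.6.1).** SEL time runs from first Run-in SEL dose to last SEL dose. It includes the run-in time of placebo-randomized and never-randomized subjects. Placebo time runs from Study Day 1 to last placebo dose. The Safety Analysis Set (3.1.5) is everyone with one Run-in SEL dose.

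**Draws.** Visit C is 21-28 days after Visit B, and Visit 1 is 7-14 days after Visit C. After that, "Subjects will have study visits on Weeks 4, 8, 12, 24, 36, 48, and every 12 weeks thereafter" (Protocol Synopsis). Appendix 2 schedules chemistry and hematology at each of these visits. Visit B samples are pre-dose.

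**The concern.** The count of subjects with an abnormality depends on how often blood is taken, not only on days exposed. Each placebo-randomized subject gives the SEL rate two or three draws for about five weeks of denominator, and then gives the placebo rate draws that are mostly 12 weeks apart. A subject counts once under each exposure type. With an inert drug, the SEL rate can therefore exceed the placebo rate.

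These are the only planned SEL-placebo incidence summaries of treatment-emergent, Grade 3-4, marked and threshold liver abnormalities. They do not compare the randomized groups, because placebo-arm and never-randomized subjects contribute to SEL.

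**Working it through.** The documents state no expected laboratory rate, so there is no planned figure to reproduce.

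**Inputs from the documents**
- 1:1 allocation, 150 per arm (Protocol 8.9.1). The number cancels.
- Run-in on SEL: 28-42 days from the visit spacing; 35 days (5 weeks) used.
- Week 4 is nominally Study Day 29 (SAP Table 3-2) with a window of ±5 days, so Days 24-34. For a placebo-randomized subject whose last run-in dose was the day before Day 1, a draw up to Day 30 counts for SEL and a later one for placebo.
- Follow-up T: at least 48 weeks (Protocol 3.3). The SAP slope horizon is Week 84.

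**Assumed, because not given:** mean follow-up, probability p of an abnormality at a draw, duration of an abnormality, and no run-in failures.

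**1. Draws at T = 84 weeks, Week 4 counted for SEL**
- SEL arm: Visits C and 1, then Weeks 4, 8, 12, 24, 36, 48, 60, 72, 84 = 11
- Placebo-randomized subjects while counted as SEL: C, 1, Week 4 = 3
- Placebo: Weeks 8 to 84 = 8

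**2. No drug effect, equal and independent chance at every draw**

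Ratio = {[1-(1-p)^nSEL + 1-(1-p)^nRun-in]/(T+10)} / {[1-(1-p)^nPlacebo]/T}

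- Small p, 84 weeks: (14/94)/(8/84) = 1.56
- Small p, 48 weeks: (11/58)/(5/48) = 1.82
- p = 0.20, 84 weeks: [(0.914 + 0.488)/94]/(0.832/84) = 1.51

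The ranges below cover p from 0.001 to 0.20, Week 4 counted for SEL or for neither group, and with or without one extra draw after end of treatment:

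| Follow-up (weeks) | Ratio |
|---|---|
| 48 | 1.37-1.82 |
| 60 | 1.36-1.71 |
| 84 | 1.32-1.56 |
| 96 | 1.30-1.51 |
| 120 | 1.27-1.46 |

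If every Week 4 draw fell on Day 31 or later and counted for placebo, the small-p value at 84 weeks would be (13/94)/(9/84) = 1.29.

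**3. How much is only the uncounted tail?** The SEL numerator runs 30 days (4.29 weeks) past last dose, while its denominator stops at last dose. Two SEL periods give 8.57 weeks. For placebo, the 30 days lost at the start offset the 30 gained at the end.
- 84 weeks: (94+8.57)/94 = 1.09, leaving 1.56/1.09 = 1.43
- 48 weeks: (58+8.57)/58 = 1.15, leaving 1.82/1.15 = 1.58

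Correcting the denominator alone therefore does not remove the excess.

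**4. Duration.** A simulation used random onsets, no drug effect, the SAP counting rules, visit windows and end-of-treatment draws, with 48-week, 84-week and mixed follow-up:

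| Episode length | Ratio |
|---|---|
| 3-7 days | 1.33-1.53 |
| 14 days | 1.24-1.35 |
| 30 days | 1.14-1.21 |
| 90 days | 1.00-1.07 |
| One year or permanent | 0.95-1.01 |

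Hand check, permanent change at a low constant onset rate, 84 weeks: placebo detects onsets over 5+84 = 89 weeks, because a run-in onset is still present after Day 31. The SEL arm also detects 89. Placebo-randomized subjects add 5 to 9 weeks to SEL, depending on Week 4. With 7, the ratio is [(89+7)/94]/(89/84) = 0.96; with 5 it is 0.94 and with 9 it is 0.98.

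Hand check, every episode exactly 30 days, nominal schedule, 84 weeks: count the onset days that some draw would catch.
- Week 4 to SEL: SEL arm 299, placebo-randomized on SEL 63, placebo 238; [(299+63)/94]/(238/84) = 1.36
- Week 4 to placebo: 299, 35 and 266; [(299+35)/94]/(266/84) = 1.12

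The simulated 1.14-1.21 lies inside this bracket.

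**5. Same subjects abnormal at every draw:** (2/58)/(1/48) = 1.66 at 48 weeks; (2/94)/(1/84) = 1.79 at 84 weeks.

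**The case against.** **Size.** An equal chance at every draw describes transient abnormalities only. Protocol 7.5.5 expects progressive kidney decline in this population, and SAP 7.2.2 grades creatinine and cystatin C against baseline. For lasting changes the ratio is near 1.0 or slightly below. This stands. A reader might infer a spurious SEL excess for nearly every analyte; the duration results do not support that.

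**Other output.** SAP 7.2.1 summarizes every central laboratory test by treatment group and visit, with line plots for creatinine, cystatin C, liver tests and hematology. Sections 7.2.2.3 and 7.2.3 add listings of Grade 3-4 abnormalities and of subjects meeting a liver criterion. The by-visit summaries compare randomized arms at the same draws. A reader might infer that a real SEL signal could not be told from the artefact; that goes too far. Still, medians by visit and listings are not an incidence table by arm, so the check is partial.

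**Status.** SAP 7.2 plans no formal testing of laboratory data, and no endpoint or decision rule uses these rates. For short-lived abnormalities the bias overstates SEL risk and does not hide harm. This limits the severity.

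**Intent.** Attributing run-in events to SEL is deliberate. Protocol 8.6 includes run-in data and summarizes by drug received. That supports reporting them under SEL, but not dividing by time without regard to draw frequency. Protocol 8.6.3 asks for incidence by treatment group, while the SAP uses exposure type and states in 7.7 that nothing deviates.

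**Conclusion.** The concern holds, with a size that depends on conditions the documents do not give. With no drug effect, the planned SEL:placebo ratio is:
- about 1.3-1.5 for short-lived abnormalities at roughly 60-96 weeks of follow-up (the equal-chance model reaches 1.71 at 60 weeks in its least favourable setting);
- up to about 1.8 at 48 weeks, or for abnormalities present at every draw;
- about 1.15-1.2 for month-long abnormalities;
- about 1.0 or slightly below for new-onset persistent or progressive ones, such as a creatinine rise.

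These figures rest on a 35-day run-in, 1:1 arms, the scheduled draws, and assumed per-draw probabilities, durations and follow-up. Run-in failures, whose number is not stated, would add further to SEL draw density. Because the bias differs by analyte, no single correction factor applies and a reader cannot recover the true contrast from these tables. They are descriptive and can be partly checked against other output, so this should be fixed but does not threaten the trial's main conclusions.

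**What to change.** In SAP 7.2.2.3 and 7.2.3:

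1. Compare SEL with placebo by randomized arm over the same scheduled draws, from Study Day 31 to last dose plus 30 days, for treatment-emergent, Grade 3-4, marked and liver-test abnormalities. Give number and percentage. Because follow-up varies, also give a rate whose person-time covers the same window as its numerator. With an equal chance per draw, no drug effect and similar follow-up, the expected ratio is 1.0 by construction.
2. Report Days 2-30, including the nominal Day 29 Week 4 draw, by randomized arm, labelled as SEL washout for placebo-randomized subjects. Without this, those results would fall in neither of the other tables.
3. Report first Run-in SEL dose to Day 1 as a single-group SEL table that includes non-randomized subjects.
4. If a pooled SEL-exposure rate is kept, label it as non-randomized and do not set it against placebo.

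The cost is SAP wording and one or two more table layouts from data already collected. Run-in SEL abnormalities leave the comparative rate but stay visible in their own table. The change should be made before unblinding.
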